9.7.2 Main analysis

For the primary effectiveness outcomes incidence rates (events per 1,000patients-years) with corresponding 95% confidence intervals (CI) will be calculated. This will be evaluated by a matched Cox proportional hazards regression model for counting processes, which allow the follow-up time to be divided into several periods and therefore control for baseline and time-dependent covariates, using the full observational period of available data, i.e. up to 11 years of follow up. The Cox proportional hazards regression will take into account the fact that individual matching (1:1) will be performed by considering the exposed patient and his/her matched controls as one stratum and including this as a stratum in the Cox proportional hazards model. Additional variables will be included in the model if available. The cumulative incidence plots will be accompanied by number of patients at risk at different time points during follow-up. For (possibly) repeating events (such as exacerbation event) additionally a Poisson regression model will be fitted for the number of events (taking into account the matching). Time in the study will be included as an offset variable in the model. The cox and Poisson models will be adjusted for unbalanced PS-variables at baseline.

The outcome will be analyzed separately for each:

- 1) Primary outcome
 - Comparison of pneumonia incidence in COPD patients using LAMA and ICS/LABA
 - Comparison of exacerbations frequency and rate in COPD patients using LAMA and ICS/LABA : moderate or severe exacerbation

Proprietary confidential information © 2022 Boehringer Ingelheim International GmbH or one or more of its affiliated companies

[figure not shown]
- Comparison of time to start triple combination therapy (time from initial 'LAMA mono' or ICS+LABA' to 'LAMA+LABA+ICS' combination) in COPD patients using LAMA and ICS/LABA

2) Secondary outcome

- Comparison of all-cause mortality differences in COPD patients using LAMA and ICS/LABA
- Comparison of lung cancer incidence in COPD patients using LAMA and ICS/LABA
- Comparison of health care utilization: Medical cost / No. of prescriptions, visits and hospitalizations (hospitalization mainly due to severe exacerbation of COPD)

Health care utilization

Health care utilization outcomes will be analyzed separately in each treatment group. Analyses will be conducted for 1)total health care expenditure 2)COPD-related utilization and cost for all of the medical resource utilization and costs during the follow-up period. For outpatient services, analyses were confined to visits with the ICD-10 code of COPD (J43.x–J44.x, except J430) with the prescription of COPD-related medication. For inpatient services, analyses were confined to admission with ICD-10 code of COPD or COPD-related disease (pneumonia: J12.x–J17.x, pulmonary thromboembolism: I26, I26.0, and I26.9; dyspnea: R06.0; or acute respiratory distress syndrome: J80) with the prescription of COPD-related medication. Medical costs per person per year will be reported overall and separately based on type of service: inpatient healthcare visits, outpatient healthcare visits, and pharmacy dispensations. This involves calculating the average cost among members who are alive in the beginning of a month.

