9.3.2 Outcomes

9.3.2.1 Primary outcomes

Primary endpoint

- Recorded pneumonia based on 1)ICD-10 code (J12.x-J18.x, J69.0, J84.9, B96.0, J85.1) AND 2) CPT code of chest x-ray(71045-71048) or chest CT(71250,71260,71270,G0297) AND 3) prescription of antibiotics for pneumonia in Korean Guideline) incidence rate per year
- Frequency rate of COPD exacerbation per year
 - Moderate exacerbation: recorded as when COPD patients visited outpatient clinics with an ICD-10 code of COPD and systemic steroid medication and/or antibiotics were prescribed (within the first year after initial prescription of inhalers)
 - Severe exacerbation: when COPD patients visited the emergency room or were admitted to hospital with an ICD-10 code of COPD(*due to COPD worsening*) and were prescribed systemic steroid medication and/or antibiotics (within the first year after initial prescription of inhalers)
- Time to start triple combination therapy ICS/LABA/LAMA)
 - Time to add LAMA in patients with using ICS/LABA or, time to add ICS/LABA in patients with using LAMA before.

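### The primary exacerbation endpoint is a yearly rate, but the plan leads with a Cox model, adds the count model only as an extra, and names neither as the estimate that answers the objective

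*Combined protocol and SAP*

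**What the plan says.** **Endpoint.** Protocol Section 9.3.2.1 lists as primary "Frequency rate of COPD exacerbation per year". The moderate and the severe definitions both limit counting to events "within the first year after initial prescription of inhalers". Section 9.7.2 restates the objective as "Comparison of exacerbations frequency and rate in COPD patients using LAMA and ICS/LABA : moderate or severe exacerbation".

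**Comparative model.** Section 9.7 applies matched Cox regression to every outcome. Section 9.7.2 opens with a descriptive step, "For the primary effectiveness outcomes incidence rates (events per 1,000patients-years) with corresponding 95% confidence intervals (CI) will be calculated", and continues "This will be evaluated by a matched Cox proportional hazards regression model for counting processes". It gives the purpose of that form as "which allow the follow-up time to be divided into several periods and therefore control for baseline and time-dependent covariates", and the follow-up as "using the full observational period of available data, i.e. up to 11 years of follow up". Each 1:1 matched pair is a stratum.

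**Count model.** For repeating events, with exacerbation as the example, "additionally a Poisson regression model will be fitted for the number of events". Time in the study is the offset and the matching is to be taken into account.

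**Not stated.** The protocol does not say which of the two comparative results is primary for exacerbations, whether second and later exacerbations enter the Cox model, or what variance allows for repeated events in one patient.

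**The concern.** A yearly frequency is a count per unit of person-time, and its natural contrast is a rate ratio. The model that estimates a rate ratio directly is the Poisson model, which is planned as an addition. The model that comes first is Cox, with event handling left open and a follow-up that can be eleven times the window in the endpoint definition.

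One primary endpoint will therefore have two comparative estimates that can differ numerically, with no rule fixed in advance for which is reported as the answer. Both ways of running the Cox model leave a problem:

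- **First events only:** the hazard ratio ignores repeat exacerbations, and it drifts from the rate ratio because patients at high risk leave the risk set early.
- **All events:** the point estimate can track the rate ratio, but a model-based variance treats one patient's repeated events as independent.

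**Working it through.** **Inputs.** There is no figure in the plan to reproduce. The protocol gives no exacerbation rate, expected effect or between-patient variance, and 5,000 per arm is a feasibility floor. The following are assumptions:

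- comparator rate λ = 0.5, 1 and 1.5 events per year
- true rate ratio r = 0.85
- gamma frailty with mean 1 and variance θ = 0, 0.5, 1 and 2, independent between pair members
- constant rates and no censoring before the end of the window (1 or 11 years)

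**Step 1: share of events that are first events.** With m expected events per patient, the share is [1 − (1 + θm)^(−1/θ)] / m. Over one year:

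- m = 0.5, θ = 1: 0.67
- m = 1, θ = 1: 0.50
- m = 1, θ = 2: 0.42
- m = 1.5, θ = 2: 0.33

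**Step 2: hazard ratio if Cox takes first events.** Averaged over the frailty, time to first event has survival S(t) = (1 + θλt)^(−1/θ) and hazard h(t) = λ / (1 + θλt). In the other arm λ is replaced by rλ. The hazard ratio at time t is then r(1 + θλt) / (1 + θrλt). With λ = 1 and θ = 1 it starts at 0.85 and reaches 0.85 × 2 / 1.85 = 0.92 at one year.

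The pair-stratified Cox estimate tends to ∫h₁S₁S₀dt / ∫h₀S₁S₀dt, because a pair informs the estimate only while both members are event-free. The unstratified estimate tends to the value at which the expected Cox score is zero. Numerical integration over λ = 0.5 to 1.5 gives:

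| θ | 1 year, unstratified | 1 year, pair-stratified | 11 years, unstratified | 11 years, pair-stratified |
|---|---|---|---|---|
| 0 | 0.850 | 0.850 | 0.850 | 0.850 |
| 0.5 | 0.863–0.876 | 0.862–0.872 | 0.891–0.896 | 0.878 |
| 1 | 0.872–0.891 | 0.871–0.885 | 0.910–0.917 | 0.895–0.897 |
| 2 | 0.886–0.908 | 0.884–0.902 | 0.928–0.937 | 0.915–0.920 |

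The pair-stratified columns match the stratification that Section 9.7.2 describes. On the log scale, λ = 1 and θ = 1 over one year gives ln(0.880) / ln(0.85) = 0.79, a shrinkage of about 21%. Censoring before 11 years would place the result between the two windows.

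**Step 3: variance if Cox takes all events.** With equal follow-up within pairs, the pair-stratified estimate is the ratio of total events. A simulation of 5,000 pairs over one year (200 runs, r = 0.80, λ = 0.8, θ = 1) gave a mean of 0.803, so the point estimate is close to the rate ratio.

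- The empirical standard error of the log ratio was 0.030.
- The pure Poisson value is √(1/3,200 + 1/4,000) = 0.024.
- Adding the frailty term 2θ/n = 2/5,000 gives √(0.0003125 + 0.00025 + 0.0004) = 0.031, in line with the simulation.
- A nominal 95% interval on the Poisson variance reaches 1.96 × 0.0237 / 0.0310 = 1.50 true standard errors, a coverage of about 87%.

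At λ = 1.5 the empirical and Poisson values were 0.025 and 0.017. The same shortfall applies to the planned Poisson model if its variance is left model-based.

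**The case against.** A reader might infer that the headline exacerbation result uses first events only, and that the plan therefore fails to estimate its own endpoint. The documents do not support either statement:

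- No section restricts the Cox model to first events, and a counting-process layout can hold repeat events. The stated purpose (time-splitting for covariates) and the separate count model make a first-event reading natural, but it remains an inference.
- Section 9.7.2 never calls the Cox hazard ratio the headline or the Poisson result supportive. Calling the count model additional may mean only that repeating events need a further model.
- The incidence rates and the Poisson model with an offset do target a rate, so a matching analysis is planned.

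The size in Step 2 also rests wholly on assumed heterogeneity. At variance 0 there is no gap, and in every scenario the estimate moves toward the null without changing direction.

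Finally, Section 9.7 defers detailed methods to an SAP, where event handling and variance estimation could normally be settled. That answers only part of the point. The same section says that major modifications of primary endpoint definitions or analyses would go into a protocol amendment, so the choice of primary estimate belongs at protocol level.

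What survives is that the primary estimator is unnamed, the event handling is unstated, and the two follow-up windows disagree.

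**Conclusion.** The point holds as a gap in specification that a change of method closes. The plan has a suitable estimator for the exacerbation rate but does not make it the primary one, and it leaves the model that leads open to two readings.

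Under a first-event reading, with an assumed rate ratio of 0.85 and 0.5 to 1.5 events per year, the one-year hazard ratio is 0.85 with no heterogeneity, 0.86 to 0.88 at frailty variance 0.5, and 0.87 to 0.91 at variance 1 to 2. Over 11 years it is about 0.89 to 0.94 at variance 0.5 to 2 without pair strata, and 0.88 to 0.92 with them. Under an all-events reading, the point estimate is close to the rate ratio but the interval is too narrow unless the variance is robust. These figures show what could happen and do not predict the result of this study. The finding that the estimator is unnamed does not depend on them.

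The change should be made before the outcome comparison is run.

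**What to change.** In Section 9.7.2:

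1. State that the primary estimate for exacerbations is the rate ratio from the count model, with log person-time as offset and robust variance clustered on matched pair. Each patient belongs to one pair, so this covers both overdispersion and the matching.
2. State that the Cox hazard ratio is for time to first exacerbation and is supportive.
3. Reconcile the first-year window in Section 9.3.2.1 with the full follow-up in Section 9.7.2, and say that the count and its offset cover the same window.
4. Keep Cox as planned for pneumonia, time to triple therapy, mortality and lung cancer.

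The cost is a few sentences, since both models are already planned and no further data are needed. The downside is a wider confidence interval than a model-based Poisson variance would give: by 0.031 / 0.024, or roughly 30%, in the Step 3 illustration, and less with lower rates or less heterogeneity. That extra width is uncertainty that the narrower interval would leave out.

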9.2 SETTING

The study will be conducted in a general practice setting, Korea National Health Insurance claim data & mortality data from the Bureau of Statistics, which includes computerized medical records of more than half million patients in South Korea. The maximal observation period will be from Jan 2005 to Apr 2016.

- Inclusion criteria
 - Diagnosed with COPD [**based on ICD-10 code(J43.x-44.x except J430), as the primary or within the fourth secondary diagnosis and initiated LAMA or ICS/LABA more than twice a year from Jan 1, 2005 to Apr 30 2016**].
 - Age >55 years old as of 2005 when enroll started
- Exclusion criteria
 - Prescription history with any long acting bronchodilator for maintenance therapy (the patient should be inhaler naïve) from 2002 to 2005.
 - Prescription history with ipratropium bromide
 - Prescription history with Leukotriene receptor antagonist(LTRA) or ICS
 - Prescription history of LABA/LAMA FDC
 - Patients with lung cancer, IPF, ILD or lung transplantation at the time of COPD diagnosis

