9.5 STUDY SIZE

In 2008~2013 NHI database, approximately 200,000 patients per year with COPD were diagnosed using COPD diagnostic code and a prescription for COPD medications (LAMA, LABA, ICS + LABA, SAMA, SABA, SAMA + SABA, PDE-4, systemic beta agonist, theophylline). In COPD patients, the use of LAMA and ICS/LABA was 26 to 37%, respectively. We expect the study to include a minimum of 5,000 patients per arm, a conservative estimate.

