9.7 DATA ANALYSIS

The study population consists of COPD patients that have received LAMA and ICS/LABA treatment. The study consists of three stages: a) identification and extraction of LAMA-exposed and ICS/LABA-

exposed cohort, b) matching between LAMA-exposed and ICS/LABA-exposed and c) descriptive analysis of cohorts and analysis of outcomes.

Detailed methodology for summary and statistical analyses of data generated in this study will be documented in an SAP. The SAP may modify the plans outlined in the protocol; any major modifications of primary endpoint definitions or their analyses would be reflected in a protocol amendment.

For the purpose of this study, analyses will be conducted using SAS statistical software and R. To address the imbalance of potential confounders between LAMA ICS/LABA groups, we matched treatment groups using propensity scores estimated as by multiple logistic regression analysis *based on* as age, sex, socioeconomics status, *Charlson Comorbidity Index*, and asthma, history of COPD exacerbation. Demographics and clinical characteristics will be tabulated. Frequencies and percentages will be presented for categorical variables. For continuous variables, means, standard deviations, and ranges, or medians and inter-quartile ranges, will be reported as appropriate. We used a standardised difference to compare baseline characteristics between COPD patients who were treated with LAMA and those treated with ICS/LABA. The matched Cox proportional hazards regression analyses will be used to estimate hazard ratios (HRs) HRs and 95% confidence intervals (95% CIs) for all outcomes. For (possibly) repeating events (such as *exacerbation event*) *additionally* a Poisson regression model will be fitted for the number of events (taking into account the matching). The cox and Poisson models will be adjusted for unbalanced PS-variables at baseline. Mortality was estimated by the Kaplan-Meier method, and results were compared between groups using the log-rank test.

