9.7.1 Analysis Dataset : Patients selection

The matching between LAMA[Spriva® HandiHaler® Respimat® (Tiotropium Bromide Monohydrate)] and ICS/LABA are performed by sex, age category (5 year spans above 55 years), years since diagnosis of COPD, as available in the database, and propensity score.

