9.7.1.1 Propensity score methodology

The propensity score will model the likelihood among COPD patients of receiving LAMA and ICS/LABA. The model for the propensity score will to the extent possible include the following elements:

- 1) Age and sex
- 2) Socioeconomic status (e.g. income, educational level, single living)
- 3) History of COPD exacerbation
- 4) Charlson Comorbidity Index
- 5) History of asthma

A logistic regression analysis will be performed on the identified COPD patients where treatment with LAMA and ICS/LABA groups is the dependent, dichotomous variable and the independent variables are listed above (age, sex and history of COPD exacerbation et al.). Based on this analysis, the propensity score is calculated for each patient. For subgroup analyses, PS matching and evaluation of its success, as presented below, will be re-done as covariate balance is not automatically maintained in sub-cohorts.

Smoking may be an important confounder in COPD but smoking status is usually not available in the databases at all. If smoking status is confirmed to be available, the data will be analysed with and without smoking status included in the model and the magnitude of the confounding effect assessed (sensitivity analysis).

PS matching will be done in a 1:1 ratio using the nearest-neighbor algorithm, using calipers of width equal to 0.2 of the standard deviation of the logit of the PS (matches of the main exposure sub-cohort and the comparator sub-cohort are formed if the caliper width is not exceeded for the logit of PS). For LAMA-exposed patient to ICS/LABA-exposed patients will be selected within the same matching interval of the propensity score. The distribution of propensity scores will be examined between LAMA-exposed and eligible ICS/LABA-exposed. In the matching procedure, matched comparator sub-cohort patients (ICS/LABA) will be removed from the pool of eligible patients among the comparator sub-cohort so that a matched patient is no longer available for consideration as a potential match for another exposed patient.

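### Stratifying the Cox model on each 1:1 matched pair discards events after the partner has left the risk set; under assumed staggered follow-up this costs about one third to one half of first events for the full-follow-up outcomes

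*Combined protocol and SAP*

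**What the plan says.** Section 9.7.1.1 of the protocol: "PS matching will be done in a 1:1 ratio using the nearest-neighbor algorithm". Section 9.7.1 says that the matching is "performed by sex, age category (5 year spans above 55 years), years since diagnosis of COPD, as available in the database, and propensity score". Calendar date of initiation is not in that list.

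Section 9.7.2 handles the matching in the Cox model by "considering the exposed patient and his/her matched controls as one stratum and including this as a stratum in the Cox proportional hazards model", "using the full observational period of available data, i.e. up to 11 years of follow up". Section 9.7 extends this to all outcomes: "The matched Cox proportional hazards regression analyses will be used to estimate hazard ratios". Covariates with a standardised difference above 0.1 after matching are added to the model. A robust variance clustered on the pair is not mentioned.

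Three other statements bear on the point. Moderate and severe exacerbations are defined "within the first year after initial prescription of inhalers" (section 9.3.2.1). Repeating events also get a Poisson model with a time offset (section 9.7.2). Mortality also gets Kaplan-Meier curves and a log-rank test, with no stratification stated (section 9.7).

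On follow-up, section 9.2 says "The maximal observation period will be from Jan 2005 to Apr 2016". There is no censoring rule for discontinuation or switching, and no expected event rate or hazard ratio.

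**The concern.** In a Cox model each event is compared with the members of its own stratum who are still at risk. With two people per stratum, once one has died, been censored or had a first event, nothing that later happens to the other enters the likelihood. Patients may start treatment at any time from January 2005 to April 2016 and pairs are not aligned on start date. One partner may therefore have ten years of potential follow-up and the other only one, and deaths in a COPD population aged over 55 break further pairs.

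What is at stake is precision. The data are historical and fixed, so discarded events cannot be made up by recruiting. The cost falls on the outcomes followed over the full period, and it matters most in practice where events are few.

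**Working it through.** **The plan's own figure.** The 5,000 per arm in section 9.5 is a feasibility estimate. The section's figures give 200,000 × 26% = 52,000 and 200,000 × 37% = 74,000 users per year before exclusions. With no alpha, power, hazard ratio or event rate, it cannot be turned into expected events. All rates below are assumptions.

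**Set-up.** There are 5,000 pairs (section 9.5) and the window is T = 11.33 years (January 2005 to April 2016, section 9.2). Assumed: constant control hazard λ0, exposed hazard λ1 = 1.3 λ0, other exits at rate d in both arms, entry uniform over the window.

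- First events per patient, each arm: [λ/(λ+d)] × [1 − (1 − e^(−k))/k], with k = (λ+d)T.
- Informative pairs, independent entry dates: [(λ0+λ1)/s] × [1 − 2/K + 2(1 − e^(−K))/K²], with s = λ0+λ1+2d and K = sT.
- Informative pairs, same entry date: the second bracket becomes 1 − (1 − e^(−K))/K.
- Stratified variance of the log hazard ratio: 1/n10 + 1/n01, the informative pairs in which the exposed or the control patient fails first.
- Approximate ratio of interval widths (log scale): 1/√(1 − share of events lost).

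**Example, 5% per year, independent entry, d = 0.** Events: k = 0.5665 gives 0.2365 × 5,000 ≈ 1,183 in controls; k = 0.7365 gives 0.2923 × 5,000 ≈ 1,461 in exposed; total 2,644. Informative pairs: K = 0.115 × 11.33 = 1.303 gives 0.323 × 5,000 ≈ 1,615. Loss = 1 − 1,615/2,644 = 39%; width ratio = 1/√0.611 = 1.28. Simulation agrees: 2,639 events, 1,605 informative, 39% lost, ratio 1.29.

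**Limits.** For rare events with independent uniform entry, mean follow-up is T/2 per patient, but both partners are at risk for only T/3 on average, so the loss is 1/3 and the ratio 1.22. If independent exponential censoring dominates, the loss is 1/2 and the ratio 1.41.

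**Range over assumed rates.**

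| Follow-up within pairs | Other exits | Event rate per year | First events lost | Interval wider by |
|---|---|---|---|---|
| Independent entry | none | 0.2, 2, 5, 10, 30% | 33, 36, 39, 42, 48% | 23, 26, 29, 32, 40% |
| Independent entry | death 0–6%/yr | 0.2–5% | 33–43% | 23–33% |
| Independent entry | 10%/yr | 0.2–30% | 43–49% | 33–40% |
| Same start date | death 0–6%/yr | 0.2–5% | 1–27% | 0–18% |
| Same start date | 10%/yr | 0.2–30% | 23–44% | 14–34% |
| First year only | none | up to 30% | 0–14% | 0–8% |
| First year only | 50%/yr | up to 30% | 21–28% | 13–18% |

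The first-year row without other exits follows from loss = (1 − e^(−hT))/2 with T = 1 when both hazards equal h. At h = 0.3 this is 13%, and about 14% with the exposed hazard 1.3 times higher.

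**What it means for an interval.**
- Rare outcome, assumed 0.2% per year, no other exits: about 132 events become 88. The 95% factor exp(1.96 × √(4/events)) goes from 1.41 to 1.52.
- Common outcome, assumed 5% per year with 6% per year mortality, hazard ratio 1.2 and pair frailty variance 0.25 (300 simulated data sets): the standard error is 0.0434 unstratified and 0.0591 stratified. The 95% intervals are 1.10–1.31 and 1.07–1.35. The robust standard error matched the empirical spread (0.0434 against 0.0427).

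**Different targets.** If partners share strong unmeasured risk, the two models estimate different hazard ratios. With pair frailty variance 1 and 10% per year, the within-pair value was 1.29 and the marginal value 1.23. Width ratios in such cases (1.29 to 1.77 for frailty variance 0.5 to 1) are not a pure measure of efficiency.

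**The case against.** Pair stratification is a recognised analysis for matched data. It gives each pair its own baseline hazard and compares partners only while both are at risk. Balance at baseline does not guarantee balance in later risk sets over 11 years, and the stratified model tolerates censoring that depends on the matching factors. This stands, and it is the reason to keep the model as a sensitivity analysis. It does not make pair strata necessary: section 9.7.1.1 judges the matching by group-level balance, and clustering the variance on the pair still accounts for it.

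A reader might infer a flat loss of about 40% of events, with intervals 30% wider, on every time-to-event outcome. The documents do not support that. They give no rates, and these figures fit only one scenario: independent entry, long follow-up and about 5% per year. First-year exacerbations lose little if follow-up is complete. In the counting-process form of section 9.7.2, a recurrent event need not end a patient's time at risk. The Poisson model can use every event, and the log-rank test as written uses every death.

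Nor does lung cancer lose proportionally most. At an assumed 0.2% per year the share lost is the lowest in the first row of the table; the loss matters there because few events are left.

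The common-outcome example reaches the same conclusion under either model, and "We expect the study to include a minimum of 5,000 patients per arm, a conservative estimate" implies that the real cohort may be larger. Both points stand and limit the severity.

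**Conclusion.** The concern holds as a conditional point about efficiency. The plan does stratify on each pair, and it does not align start dates. If entry dates differ within pairs, about one third to one half of first events carry no information, and intervals are about 23% to 40% wider for pneumonia, time to triple therapy, all-cause mortality and lung cancer. The range rests on assumed event rates of 0.2% to 30% per year, uniform entry over 11.33 years, constant hazards, and none to 10% per year of other exits. The upper end needs frequent events or frequent other exits. With similar start dates the loss is smaller unless events or other exits are frequent.

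A reader might also infer that the stratified hazard ratio is biased or the method wrong. Neither follows: it is valid for a within-pair hazard ratio, and the choice is partly one of estimand. The change is worth making because it is cheap and the discarded events cannot be replaced. It would also bring the hazard ratio into line with the incidence rates and log-rank test reported beside it, which use all events.

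**What to change.** For pneumonia, time to triple therapy, all-cause mortality and lung cancer, specify as the main model an unstratified Cox model. It should contain treatment and any covariate with a standardised difference above 0.1 after matching, with a robust sandwich variance clustered on the matched pair. Keep the pair-stratified model as a sensitivity analysis, and report the events and informative pairs that it uses. State the censoring rules, since the loss depends on them.

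The cost is one line of SAS or R code and a short change of wording. Section 9.7 lets the SAP modify the plan but requires a protocol amendment for a major change to the analysis of a primary endpoint, so the sponsor should decide whether this counts as one. The small downside is that the main hazard ratio becomes marginal rather than within-pair; the SAP and report should say so.
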